10. POTENTIAL BENEFITS TO SUBJECTS

There is no anticipated benefit to subjects who take part in this research study.

11. COSTS FOR PARTICIPATION

There are no anticipated costs for study participation.

12. PAYMENT FOR PARTICIPATION

Study subjects will be compensated \$50 by check sent from the University of Rochester Medical Center to that subject's home address. Study medication—either daridorexant or placebo—will be provided and administered free of charge to the patient.

13. SUBJECT WITHDRAWALS

Definition of treatment failure or subject removal criteria:

All consented subjects will be retained in the study, and all primary analyses will be performed per protocol. All daridorexant arm subjects who develop postop delirium represent patients for whom daridorexant failed to prevent delirium. However, we do not expect daridorexant to prevent all delirium, so we would not use the term "treatment failure" to describe incident delirium in these patients. We would remove patients from the study only in the event of serious adverse events.

What happens to subjects when study ends or if a subject's participation in the study ends prematurely:

Patients will be thanked for their participation in the study and will be advised to call the PI with any questions. Study agent—either daridorexant or placebo—is being provided for up to the first three nights after surgery, but we will not be providing this to those who discharge prior to this. Early discharges are not only rare but indicate that the patient is doing so well that they no longer require inpatient level of care, which implies that they would not have delirium at the time.

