1. PURPOSE OF THE STUDY

Purpose: This feasibility study is designed to inform and ultimately support a grant application for funding for an adequately powered randomized, clinical trial (RCT) of daridorexant to prevent postoperative delirium. In this phase 2 study, we will test the following specific aims:

Aim 1: To demonstrate that we can recruit subjects for a placebo-controlled RCT of daridorexant to prevent postoperative delirium.

Target: We will enroll up to 16 subjects. Our recruitment goal is four subjects per month, for a total of 12 subjects completing the protocol.

Aim 2: To demonstrate that we can deliver study compounds to subjects per our proposed methods, including successful use of the OnCore Enterprise Clinical Trial Management System. *Target*: All doses of study compound will be delivered successfully.

Aim 3: To demonstrate successful capture of preoperative, intraoperative, and postoperative data relevant for analyses during the conduct of this trial.

Target: We aim for 100% data capture, including subject retention through all doses of study compound.

Aim 4: To document all potential adverse events (AEs) and serious adverse events (SAEs). *Target*: All subjects will be evaluated daily after receipt of study compound for AEs and SAEs.

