4. STUDY DESIGN

This double-blind, parallel-group trial will randomize patients having cardiac surgery—either surgical aortic valve replacement (SAVR) or coronary artery bypass graft (CABG) surgery—to oral daridorexant 50 mg or identical-appearing placebo. The primary outcomes are feasibility and safety. Study subjects will provide written informed consent after receiving a complete description of the study. See Figure 1 below for a timeline of study assessments (not to scale).

[figure not shown]

Figure 1 – Timeline of Study Assessments

Abbreviations: 3D-CAM, 3-minute Diagnostic interview for the Confusion Assessment Method; CAGE-AID, CAGE [an acronym for "Cut down, Annoyed, Guilty, Eye-opener"] Adapted to Include Drugs; **POD**, postoperative day; **PON**, postoperative night; **TICS**, Telephone Interview for Cognitive Status *25 mg for subjects on a moderate 3A4 inhibitor (see 4.2 STUDY INTERVENTION below for details)

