
Plan for breaking the blind for a subject

If a patient has a medical emergency that requires immediate clinical care for stabilization, including angioedema, anaphylaxis, attempted suicide, or any other condition that is considered—in the opinion of the PI or the primary medical team—as potentially attributable to daridorexant, we will contact the IDS pharmacist to identify whether the patient has received daridorexant or placebo. If this occurs, the subject will be withdrawn from the study, and this will be reported to the RSRB and DSMB.

Legal risks such as the risks that would be associated with breach of confidentiality:

As with any study incorporating research into clinical care, there is a small but real risk of unintentional release of HPI. We will make every effort to secure data and study records under double lock/key and encryption in keeping with institutional standards to prevent this from occurring.

Version date: 2/3/2025

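### Section 13 puts all primary analyses on a per-protocol basis, which fits badly with primary outcomes of feasibility and safety that have to count missed doses, withdrawals and removals

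*Protocol*

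**What the plan says.** On outcomes, Section 4 says: "The primary outcomes are feasibility and safety". Section 1 sets the targets. Aim 2: "All doses of study compound will be delivered successfully". Aim 3: "We aim for 100% data capture, including subject retention through all doses of study compound". Aim 4: "All subjects will be evaluated daily after receipt of study compound for AEs and SAEs".

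On the analysis set, Section 13 says: "All consented subjects will be retained in the study, and all primary analyses will be performed per protocol". Section 17 regards Aims 1 to 3 as unsuited to formal statistical analysis and names no other set.

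The protocol foresees doses that will not be given. For early discharge, Section 13 says study agent is offered for up to three nights, "but we will not be providing this to those who discharge prior to this". Section 4.2 allows dosing up to midnight for a subject extubated late, so a subject extubated after that misses the first dose.

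On removal, Section 13 says: "We would remove patients from the study only in the event of serious adverse events". The plan for breaking the blind in Section 9 covers medical emergencies needing immediate stabilising care, "including angioedema, anaphylaxis, attempted suicide, or any other condition that is considered" by the investigator or the treating team to be potentially attributable to daridorexant. Every subject unblinded in this way is withdrawn.

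**The concern.** A conventional per-protocol set keeps subjects who took the treatment and completed follow-up as planned. In an efficacy trial that is one possible sensitivity set. Here the outcomes are whether doses are delivered, whether subjects stay and what harm occurs. A subject who misses a dose or is withdrawn is the event being counted, so excluding that subject removes the failure from both numerator and denominator.

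The trial's whole output is a small set of descriptive proportions meant to support a grant application for a powered trial. With at most 16 subjects and targets of 100%, one subject decides whether a target is met. A favourable denominator could carry into planning assumptions on dosing, retention and safety.

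**Working it through.** The protocol gives no calculation on this point, so there is no figure to reproduce. The check sets the texts side by side and then shows how far the denominators can diverge.

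**Text.** Section 4 defines what is primary and Section 13 says how everything primary is analysed, so together they assign a per-protocol set to feasibility and safety. The Section 1 targets are worded over all doses, retention through all doses and all subjects. The first clause of the Section 13 sentence keeps all consented subjects. The second clause, read conventionally, does not.

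**Inputs from the protocol.** Up to 16 enrolled and 12 to complete (Section 1); three nightly doses (Section 4.2); block size six (Section 9's predecessor, Section 3, and Section 16).

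**Assumptions, not protocol figures.** The numbers of missed doses, non-completers and SAEs; all enrolled subjects are randomised; the per-protocol set drops any subject with a missed dose or removal.

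**1. Dose delivery when k subjects each miss one dose.** All randomised: (3N − k)/3N. Per protocol: 3(N − k)/3(N − k) = 100% for any k.

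| N | k | All randomised | Per protocol |
|---|---|---|---|
| 16 | 1 | 47/48 = 97.9% | 45/45 = 100% |
| 16 | 4 | 44/48 = 91.7% | 36/36 = 100% |
| 12 | 1 | 35/36 = 97.2% | 33/33 = 100% |
| 12 | 4 | 32/36 = 88.9% | 24/24 = 100% |

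**2. The protocol's planning numbers taken at face value.** If 16 enrol and 12 complete, retention is 12/16 = 75.0% over all enrolled and 12/12 = 100% over completers. If the four others receive 0 to 2 doses each, delivery is (36 + 0)/48 = 75.0% to (36 + 8)/48 = 91.7%, against 36/36.

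**3. One dosed subject removed for an SAE, no other SAE** (exact 95% intervals).

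| N | SAE, all dosed | SAE, per protocol | Retention, all | Retention, per protocol |
|---|---|---|---|---|
| 16 | 1/16 = 6.3% (0.2 to 30.2%) | 0/15 (0 to 21.8%) | 15/16 = 93.8% | 15/15 |
| 12 | 1/12 = 8.3% (0.2 to 38.5%) | 0/11 (0 to 28.5%) | 11/12 = 91.7% | 11/11 |

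Within one arm of 6 (two full blocks), the SAE rate is 1/6 = 16.7% against 0/5. The intervals overlap heavily. The point is that the event disappears from the summary, not that the two rates differ statistically.

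**4. Removal rules.** Angioedema and anaphylaxis fall under both rules. The Section 9 SAE list names death or suicide but not an attempt, although an attempt could qualify through prolonged hospitalisation or a needed intervention. An adverse event must be reasonably attributable to study assessments or to daridorexant. A placebo subject's emergency unrelated to assessments is therefore not an SAE as defined, yet unblinding would lead to withdrawal. The two rules differ only in cases such as these.

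**The case against.** The strongest reply is that the sentence itself resists the harmful reading. It begins by retaining every consented subject, so the phrase may loosely mean as planned. That is plausible and makes the problem conditional. It does not remove it: the two readings give different denominators, and the DSMB schedule in Section 16 treats the 12 completers as the full study sample, so a completer-based reading is not far-fetched.

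A second reply is that the neighbouring sentences concern delirium, so the primary analyses may be delirium comparisons. But Section 4 names feasibility and safety as primary, and Section 17 describes no delirium analysis.

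Third, removals that the protocol itself prescribes are arguably not deviations, so a per-protocol set need not drop them. This stands. It makes 0/15 a possible result, not an established one, and the same holds for doses omitted under the discharge and extubation rules.

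Three stronger readings may tempt a reader, and the protocol does not support them:

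- That safety events would be lost. Section 9 records them from enrolment to the final assessment and sends them to the review board and DSMB. Only a summary rate is in question.
- That the missing definition of per protocol is itself an error. It could be left to a statistical analysis plan. The problem is the choice of set.
- That the removal rules conflict broadly. Many emergencies that trigger unblinding would also meet the SAE list.

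**Conclusion.** The point holds as a stated analysis rule that suits its outcomes badly. If per protocol has its conventional meaning, the Aim 2 and Aim 3 proportions approach 100% whatever happens, and an SAE in a removed subject could drop out of the reported rate. If it means as planned, the sentence is ambiguous and should say so. A reader might infer that the sponsor has committed to a completers-only analysis; the retention clause in the same sentence does not allow that conclusion.

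The effect is confined to descriptive denominators. No hypothesis test, power figure or error rate is touched. The sizes shown rest on assumed counts and on a set that drops every subject with a missed dose or removal. The correction is worth making because it is cheap and these proportions are what the trial exists to produce. The difference between the removal rules is real, narrow and minor.

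**What to change.** Replace the per-protocol sentence in Section 13 with explicit sets:

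- **Recruitment, retention and data capture:** all consented subjects, with losses before randomisation shown separately. Restricting these to randomised subjects would drop people lost between consent and randomisation, who count for Aims 1 and 3.
- **Dose delivery:** all randomised subjects and all scheduled doses, with doses not given shown by reason, including early discharge and the extubation window.
- **Safety:** all subjects who received at least one dose, by compound received. List events between enrolment and first dose separately, because event reporting starts at enrolment.
- **Removed or withdrawn subjects:** data already collected stay in these sets.
- **Per-protocol summary:** supplementary only, if wanted.

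As a separate minor item, reconcile the retention and removal statements in Section 13 with the SAE definition and the unblinding withdrawal in Section 9. No view is taken on which removal rule is right.

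The cost is protocol wording, with no added visits or data. The reported feasibility figures may look slightly less favourable.

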14. PRIVACY AND CONFIDENTIALITY OF SUBJECTS AND RESEARCH DATA

See also Appendix I – University of Rochester Human Subject Research Electronic Data Security Assessment Form

Risks pertaining to confidentiality of data and information storage:

Study data will be collected confidentially from the patient and collateral informant. Patients will be assigned a sequential study identification number, which is used for all study purposes. Data from interviews and self-report questionnaires including consent forms will be recorded in hardcopy. All hardcopies will be permanently stored in a locked filing cabinet at SMH either in the PI's personal office or the office of study personnel. Name, date of birth, and other identifying information will be kept in a separate locked file. All data will be entered into an electronic database (REDCap, described in next paragraph) into a final dataset that will be de-identified and reside on a secure URMC server. Study personnel will have access to research data. In performing analyses, the PI may share de-identified data with any member of the mentorship team for guidance on analyses.

Study data will be collected and managed using Research Electronic Data Capture (REDCap) tools hosted at URMC.¹⁰⁴ REDCap is a secure, web-based application designed to support data capture for research studies, providing 1) an intuitive interface for validated data entry; 2) audit trails for tracking data

manipulation and export procedures; 3) automated export procedures for seamless data downloads to common statistical packages; and 4) procedures for importing data from external sources.

15. DATA / SAMPLE STORAGE FOR FUTURE USE

De-identified data will be stored indefinitely both for subsequent analyses and to support anticipated future grant applications. The data will be stored on the PI's office UR computer, UR research laptop, in a UR Box folder, and in REDCap. Upon study completion, only the PI will have direct access to deidentified study data.

16. DATA AND SAFETY MONITORING PLAN

Overview:

This Data and Safety Monitoring Plan (DSMP) specifies the procedures and rationales of the current prospective trial to ensure the safety of subjects and the validity and integrity of the data collected. The DSMP identifies who will look at the data and review any adverse events, how often, and what they are authorized to do.

For this study, the PI will be responsible for monitoring the project as the Data and Safety Monitor under advisement of an independent Data and Safety Monitoring Board (DSMB). All adverse events will be recorded and reports created by the PI in collaboration with the research coordinator.

The DSMB will include individuals with clinical experience relevant to this population and sleep pharmacology.

The risks associated with this trial are described in section 9 above.

Data and Safety Monitor:

As the Data and Safety Monitor, the PI will be responsible to maintain protocols and consent documents for this study, monitor safety issues throughout the study, and provide an overview of the quality of the accumulating data. DSM Monitor responsibilities and actions include:

- Review and approve, disapprove, or suggest modifications to the study protocols and/or consent documents to assure both scientific integrity and study adherence to human subject protection policies.
- b. Monitor, provide feedback, and report on scientific and ethical issues related to study implementation for the protection of human subjects and advise on ethical issues related to adverse events.

Data and Safety Monitoring Board:

- a. The DSMB will monitor adverse event reports for purposes of determining whether their nature, frequency and severity are consistent with expectations.
- b. The DSMB, in coordination with the PI, will report to the Research Subjects Review Board any unanticipated problems involving risks to subjects (per 45CFR46). If considered related to the study, adverse events involving risks to subjects or to others must be reported by the PI to the University of Rochester Research Subjects Review Board.
- c. The DSMB can recommend remedies or other appropriate actions such as introducing new monitoring protocols, altering inclusion or exclusion criteria, or recommending changes in the informed consent documents.

d. Ensure that the study protocol maintains patients' confidentiality in a manner that is appropriately balanced with issues of clinical care and safety.

e. Monitor data management activities. The DSMB may ask to review data relevant to quality control. This Board will review requests for interim analyses and approve, disapprove, require additional information, or defer decisions.

Schedule:

The DSMB will review study conduct and data collected after the first six enrolled subjects have completed the study and then again after the full study sample of 12 subjects have completed the study. Given block randomization with a block size of six, we expect the initial review of six subjects will include three subjects receiving daridorexant and three receiving placebo. The DSMB and study PI will decide the format of meetings. Additional meetings or telephone conferences will be held on the recommendation of the DSMB.

